Study Objective(s)	
Our goal for this study is to generate preliminary data that is needed to support an application to NIH for funding of a larger, adequately-powered study to explore whether a set of genotypes, that increase the risk for nonalcoholic fatty liver disease (NAFLD), predispose individuals to increased de novo lipogenesis (DNL) and liver fat accumulation when exposed to fructose intake.
 
Primary Objective: To determine the impact of acute and prolonged exposure of fructose on hepatic lipid accumulation in adolescents and young adults (12-40 years) with high and low genetic risk for NAFLD using liver mass resonance imaging (MRI).
 
Secondary Objective: To explore the genetic-specific effects of fructose on markers of liver fat accumulation (fibroscan⁵ and fatty liver index⁶) and serum biomarkers related to lipids, uric acid and liver function.

Test Article(s) (If Applicable)	Sugar-Sweetened beverages
Study Design	
 a. We will screen 200 Caucasian children and young adults (12-40 years) to obtain 24 children and 24 young adults who are overweight/obese and drink <14 fructose drinks/week to participate in a 3-week fructose intervention study. The 200 participants will be genotyped for 10 SNPs involved in lipid metabolism and associated with increased NAFLD risk in previously published studies^{7,8}. We will select 12 children and young adults with 15 or more risk alleles and 12 children and 12 young adults with 6 or fewer risk alleles and provide them fructose + glucose⁹ drinks who will ingest one drink (equal to 2 soft drinks) per day for 3 weeks; b. We will measure liver fat using Liver MRI^{9,10} and transient elastography (Fibroscan)⁵ at week 0 and 3;

c. Data will be analyzed using paired and unpaired students T test to differentiate the responses between the time points and between the two groups, respectively.

Specific Aim2: Determine the impact of acute exposure of fructose on hepatic *de novo* lipogenesis

- Using the cohort described in Specific Aim1, we will conduct oral fructose tolerance test at week 0 and week 3;
- We will measure liver fat using Fibroscan
- Data will be analyzed using unpaired students T test and repeated measures ANOVA to differentiate the responses between and within the two groups, respectively.

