	(2) Intervention: This part is divided into two phases. Each phase entails two visits. Phase2-visit 1: The 48 enrolled (24 in each of the high and low genetic risk group) will

visit the UNC NRI clinical suite run by the Human Research Core. They will be taken to the WakeForest imaging center for their baseline MRS scan.

Visit 2: Acute fructose challenge: The next day, they will have their initial anthropometrics and Fibroscan measurements. They will then undergo an oral fructose challenge using a protocol used by Hudgins et al¹³. The participants will be provided with a drink consisting of fructose (0.75g/kg body weight) + glucose (0.45g/kg body weight) dissolved in 24 Oz of water (equal to 2 soda cans) to be consumed within 15 minutes. Blood and urine will be sampled at baseline and 1 and 3 hours after sugar drink ingestion. During the challenge period, no other beverage (except water) or food will be allowed.

3-week intervention: The 48 participants will be provided with sugar drinks for the three week period. The drinks that need to be taken per day will contain fructose (0.75g/kg body weight) + glucose (0.45g/kg body weight) dissolved in 24 Oz of water (equal to 2 soda cans) which is similar to that provided during the acute fructose challenge⁷.

[figure not shown]
Addition of glucose to fructose in the challenge and 3-week intervention induces the lipogenic effects of fructose, alleviates gastrointestinal effects of fructose and mimics the real-life situation¹⁴. They will visit at the end of each week to collect drinks for the next week. In addition, participants will be given standardized meals for the day prior to the baseline fructose challenge. They will also be instructed to avoid alcohol, juices and sodas the previous evening.

Efficacy Evaluations	Changes in liver fat accumulation through MRI scans and fibroscan measurements, and serum concentration of other lipids, liver function markers and uric acid.
Pharmacokinetic Evaluations	N/A

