- Medical History: Information related to medical conditions, procedures and surgeries
- Modifiable activity form: Information related to physical activity, sedentary time and job activities
- Medications: Information related to prescription, non-prescription and traditional medications
- Dietary data: Combination of diet recall and food frequency questionnaire will be used to obtain detailed dietary data.

Sample preparation: A total of 24 mL of blood will be drawn at fasting at baseline, 1 hour, 3 hours, at weeks 0 and 3 by a trained phlebotomist through venous puncture. After centrifugation, the serum and plasma fractions of the blood samples will be aliquoted and stored at -80°C to measure the biomarkers listed below using standard reference procedures. All samples will be labeled and inventoried as per standard protocols. Urine will be collected at the same points as blood samples collected at baseline, 3 hour at weeks 0 and 3 will be stored at -80°C. The Human Research Core will assist with phlebotomy services

Meals: All participants will be provided standardized meal for the evening prior to participation of part 1 of phase 2.

Assessment of liver fat accumulation and stiffness: Magnetic resonance imaging (MRI): We will assess liver fat accumulation at week 0 and week 3 using the 2012 Siemens MAGNETOM Skyra 3T MRI system available at the WakeForest Translational Imaging program. If the liver fat fraction >5%¹⁰ then we will exclude the participant from further participation in the nutrient challenge.

Transient elastography: We will use transient elastography to ascertain the changes in the amount of fat in the liver. Transient elastography using a **Fibroscan®** is a non-invasive method of assessing fat accumulation in liver and liver stiffness and works on the principle of vibration controlled transient elastography⁵. A vibration of mild amplitude and low frequency is transmitted through the intercostal space using a vibrator at the skin surface. The vibration induces an elastic shear that propagates through the hepatic tissue. Using pulse echo ultrasound acquisition, the velocity of the shear wave can be determined. The shear wave, directly related to tissue stiffness and expressed in kilopascal (kPa), can be a helpful aid to clinically manage patients with liver disease. The UNC Human Research Core houses a Fibroscan and its trained technicians will help with its use for this study.

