4.6 Rescue medication administration (if applicable)

4.7 Subject Completion/ Withdrawal procedures

- Participants can voluntarily withdraw anytime during the study if they feel that they cannot continue to consume the drinks. They will be paid according to completion of phases of the study.

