6.3 Statistical Methods

Each subject will be given sugar drink containing fructose and liver MRI scan with fibroscan measurements will be taken at baseline and end of 3 weeks. Data will be assessed using descriptive measures and confidence intervals. Paired t-tests and repeated measures regression analysis will be performed to explore the significant differences between week 0 and week 3. Also, for each subject, the area under the curve (AUC)¹³ will be computed and a linear regression with AUC as the response will be performed during the acute challenge.

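### The synopsis and Section 6.3 name different analyses for the acute fructose challenge, and neither, as stated, uses incomplete time courses or tests whether the time course differs by genetic risk group

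*Combined protocol and SAP*

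**What the plan says.** Three places bear on the acute-challenge analysis.

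- **Synopsis, Specific Aim 2.** The challenge is repeated: "we will conduct oral fructose tolerance test at week 0 and week 3". The analysis is "unpaired students T test and repeated measures ANOVA to differentiate the responses between and within the two groups", and the sentence pairs methods with comparisons in that order: t-test between groups, ANOVA within groups. The only outcome that the Aim 2 bullets name is in "We will measure liver fat using Fibroscan".
- **Section 6.3.** ANOVA is not mentioned. For the challenge, an AUC is computed per subject and "a linear regression with AUC as the response will be performed during the acute challenge". No predictor is listed. A second method is reserved for the other comparison: "Paired t-tests and repeated measures regression analysis will be performed to explore the significant differences between week 0 and week 3".
- **Sampling.** The synopsis (Study Phases) says: "Blood and urine will be sampled at baseline and 1 and 3 hours after sugar drink ingestion". Section 4.2, under sample preparation, says: "A total of 24 mL of blood will be drawn at fasting at baseline, 1 hour, 3 hours, at weeks 0 and 3". That makes up to six draws per person.

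On missing data, Section 4.7 says: "Participants can voluntarily withdraw anytime during the study". There is no expected dropout rate, rule for a missed draw, covariance structure, sphericity correction or significance level.

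**The concern.** The study hypothesis (synopsis, Study Rationale; Section 2.2) is that high-risk genotypes respond more strongly to the same fructose load. For a sampled time course, that is a group-by-time question. An ANOVA run within each risk group shows whether a marker moves over time in that group, not whether the groups move differently. The t-test does compare groups, but no time point or summary is named for it. The AUC regression could compare groups if risk group were its predictor, but the plan does not say so.

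The second issue is incomplete series. Classical repeated measures ANOVA needs every sample from each participant. A three-point AUC also needs a rule when a draw is missing. The repeated measures regression in Section 6.3 might accommodate gaps, but it is tied to week 0 against week 3. If both weeks entered one ANOVA, a participant who left before week 3 would also lose a complete week 0 challenge. Section 4.7 links withdrawal to not being able to continue with the drinks, so losses may not be random. Section 6.4 intends to size larger studies from these data, so a depleted or selected subset would carry forward.

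The third and smallest issue is sphericity. The ANOVA F test for time assumes equal variances of all pairwise time differences, which is doubtful for draws at 0, 1 and 3 hours after a sugar load.

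**Working it through.** The plan gives no power, standard deviation, correlation, dropout rate or alpha, so there is no figure of its own to reproduce. Inputs from the documents are 48 participants, 24 per risk group (synopsis, Study Phases), 3 draws per challenge and 2 challenges, hence 3 × 2 = 6 draws. The missing rate per draw (3%, 5%, 10%), independence of missing draws, the 5% test level and the covariances are assumptions.

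**1. Participants lost under complete-case analysis.** With k draws and missing probability p per draw, the complete fraction is (1 − p)^k. The standard error relative to full data is 1/√[(1 − p)^k].

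| p | k | Complete | Participants lost | Expected complete of 48 | SE increase |
|---|---|---|---|---|---|
| 3% | 3 | 0.97³ = 0.913 | 9% | 43.8 | 5% |
| 5% | 3 | 0.95³ = 0.857 | 14% | 41.2 | 8% |
| 10% | 3 | 0.90³ = 0.729 | 27% | 35.0 | 17% |
| 3% | 6 | 0.97⁶ = 0.833 | 17% | 40.0 | 10% |
| 5% | 6 | 0.95⁶ = 0.735 | 26% | 35.3 | 17% |
| 10% | 6 | 0.90⁶ = 0.531 | 47% | 25.5 | 37% |

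**2. How much a mixed model recovers.** The comparison above is with full data, which no method can restore. For the 3 h minus 0 h contrast in one challenge, with p = 5% and assumed correlations of 0.5 to 0.85, the SE increase under a likelihood-based mixed model is about 2.5% to 4%, against 8% for complete cases. The gain is 4 to 5 percentage points.

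**3. Type I error of the uncorrected F test.** Simulation of 40,000 null trials with 2 × 24 participants and three times, at nominal 5% (Monte Carlo error about 0.1 point), gave these rejection rates for time and group-by-time:

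- compound symmetry: 5.1%;
- epsilon 0.875: 5.4% to 5.8%;
- epsilon 0.78: 6.1% to 6.3%;
- epsilon 0.73: 6.4% to 6.5%;
- epsilon 0.54: about 8.0%.

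The limit for three times is P(F[1,46] > 5% point of F[2,92]) = 8.5%. For one group of 24 it is P(F[1,23] > 5% point of F[2,46]) = 8.7%. A separate simulation of one group of 24 gave 5.4% at epsilon 0.89 and 8.4% at 0.53. With two levels (week 0 against week 3) the rate was about 5%, because sphericity cannot fail.

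**4. Remedies checked on complete data (2 × 24).** A Greenhouse-Geisser correction held 4.6% to 5.1%. An unstructured-covariance test of group-by-time held 4.7% to 5.1%.

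**The case against.** A reader might infer more: that the time course will be analysed by ANOVA, that incomplete participants will be discarded, and that the false-positive rate will exceed 5%. The documents do not support that reading.

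- Aim 2 does not attach ANOVA to the hourly samples. Its one named outcome, Fibroscan, is taken at two times, where sphericity is not at issue. Section 6.3 names AUC for the challenge, which makes no sphericity assumption. Computed per challenge, AUC need not lose week 0 data to a later withdrawal.
- No section says that incomplete cases are dropped or that F tests go uncorrected. Both are inferences from usual practice. AUC can also be formed from 0 and 3 hours when only the 1-hour draw is missing, given a rule.
- The between-group comparison is assigned to the t-test, which does not depend on sphericity.
- The six-sample losses are the unfavourable case. Withdrawal clusters: if an average of 10% missing per draw came entirely from dropout before week 3, 20% of participants would be incomplete (3 of 6 draws × 20% = 10% per draw), not 47%. Draws within one clinic visit may rarely be missed.
- The study is exploratory, and Section 6.4 disclaims power.

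All of this stands, and it limits the size of the point. It does not supply a single named analysis, a predictor for the AUC regression, a rule for missing draws or a test of group-by-time.

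**Conclusion.** The point holds in limited form. The synopsis and Section 6.3 disagree on the acute-challenge analysis. As written, neither tests whether the time course differs by risk group, and neither in its usual form uses an incomplete series. Those are the main grounds.

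The cost in precision is modest if each challenge is analysed alone and larger if all six draws enter together. It rests wholly on assumed, independent missing rates, and a mixed model would recover only part of it. Type I inflation is secondary. It applies only to uncorrected F tests over three or more times and, for three times, has a limit of about 8.5% (8.7% for one group of 24). The change is worth making because it is cheap and because these data are meant to inform the sample size of later studies.

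**What to change.** 1. Reconcile Specific Aim 2 with Section 6.3 so that one primary analysis of the acute challenge is named.
2. For each serum marker, replace the within-group ANOVA with one linear mixed model using all available samples. Fixed effects: age group, risk group, time (0, 1, 3 h), week (0, 3), all two-way interactions among group, time and week, and the three-way interaction. Allow participant-level correlation across weeks, with unstructured covariance over the three times, heterogeneous compound symmetry as the stated fallback, and Kenward-Roger degrees of freedom.
3. Make group-by-time the key contrast, and state in advance whether it is taken at week 0 or averaged over both weeks.
4. Keep AUC as a supporting summary, with risk group as the stated predictor and a rule for a missing draw.

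The cost is analysis wording and a slightly more complex model, with no extra data. The model is valid under missing at random, so it reduces but does not remove bias from tolerance-related dropout. A lighter alternative is AUC alone with risk group as predictor and a missing-draw rule, plus a Greenhouse-Geisser correction for any ANOVA that is kept. That settles most of the point, but it does not test the shape of the time course by group.

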Study Rationale	
Fructose consumption has dramatically increased over the past 20 years in the United States (US) and worldwide¹. High fructose intake has been shown to increase serum triglycerides, upregulate de novo lipogenesis, reduce fatty acid oxidation and decrease the clearance of very low density lipoprotein triglycerides in liver leading to nonalcoholic fatty liver disease (NAFLD)¹. Nonalcoholic fatty liver disease (NAFLD), the leading cause of chronic liver disease in the US, is characterized by fat accumulation in liver cells not caused by alcohol². A group of disorders including steatosis, nonalcoholic steatohepatitis with fibrosis and cirrhosis, NAFLD has substantially risen in prevalence over the last two decades with recent estimated prevalence being 20% among US adults and 25% in young adults (18-39 years).²
 
Although evidence has been presented for the positive relationship between fructose intake and NAFLD, the role of fructose in liver fat accumulation has been unclear. Individuals with specific genotypes seem to be more susceptible to the adverse metabolic effects of fructose. For example Hispanic children with rs738409 (GG) single nucleotide polymorphism (SNP) of patatin-like phospholipase, domain-containing 3 (PNPLA3) increased their liver fat by 23% more than CG/CC children exposed to the same amount of dietary fructose³. Similarly, adolescents with rs1260326 (TT) of glucokinase regulatory protein (GCKR) variant increased their de novo lipogenesis by 44% as compared to CC adolescents when given a sugar challenge⁴. Therefore, we hypothesize that when given the same amount of fructose individuals with specific set of genotypes will be more susceptible to increased de novo lipogenesis and liver fat accumulation than others.

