Specific Aim3: Determine the relationship between markers of DNL, liver fat accumulation and serum concentrations of lipids, uric acid and liver function markers before and after the fructose challenge

- We will measure serum concentrations of liver function markers, lipids and uric acid at week 0 and week 3;
- As in previous aims, data will be analyzed using students T test, and Pearsons correlations.

Subject Population	Inclusion Criteria
key criteria for Inclusion and Exclusion:	
 Subjects between 12 and 40 years No history of alcohol abuse (> 7 drinks per week) History of fructose intake of < 14 drinks per week Caucasian ethnicity BMI > 25kg/m² – 32kg/m² or 85th -99th percentile but otherwise healthy
	Exclusion Criteria
	
 ages < 12 and > 40 years Pregnant/lactating known alcohol abuse or fructose intake > 14 drinks per week not of Caucasian ethnicity glucose levels > 100 mg/dl if fasting, > 140mg/dl if within 2 hours post meal and > 200 mg/dl if random sample taking anti-hypertensive, anti-diabetic, uric acid and/or lipid-lowering medications known diagnosis of diabetes, fructose intolerance, chronic kidney disease, NAFLD or any liver-related disease, hypertriglyceridemia, polycystic ovary syndrome, hypothyroidism, obstructive sleep apnea, hypopituitarism and hypogandism BMI < 25kg/m² or > 32 kg/m² or < 85th or > 99th percentile Liver fat fraction >5% as per baseline MRI scan
Number Of Subjects	200 for first phase and 48 for the second and third phases
Study Duration	The first phase will be about 30 minutes and the second and third phase will be divided into two visits. Both visits in both phases will be about 3.5 hours each.
Study Phases	(1) Screening: We will screen participants for eligibility to participate in the study based on the inclusionary/exclusionary criteria specified above. The 200 children and young adults selected to participate will provide saliva which will be used to extract DNA and then genotype 10 SNPs. These SNPs are selected based on their association with de novo lipogenesis (DNL) or liver fat accumulation in previously published studies in Caucasians. We will select 12 children and 12 young adults with more than 15 risk alleles and 12 children and 12 young adults with less than six number of risk alleles.
Screening	
Study Treatment	
Follow-Up	

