We will conduct a spot glucose check using a glucometer (Accu-Chek, Roche Diagnostics, CH) to check that the glucose levels of the participants are in the normal range (fasting < 100mg/dl, post meal < 140 mg/dl and random < 200 mg/dl). The exclusion criteria includes ages < 12 and > 40 years, known alcohol abuse or fructose intake > 14 drinks per week, not of Caucasian ethnicity, glucose levels > 100 mg/dl if fasting, > 140mg/dl if within 2 hours post meal and > 200 mg/dl if random, and known diagnosis of diabetes, fructose intolerance and chronic kidney disease.

We will collect saliva from the eligible 200 children and young adults, extract DNA and genotype 10 SNPs shown in Table1.

Genotyping: SNPs will be genotyped from DNA extracted from saliva. Genotyping will be conducted in [name] lab using TaqManSNP genotyping assays (Applied Biosystems, Foster City, CA). The minor allele frequencies (MAFs) of these SNPs range between 7 and 49% based on Caucasian ethnic background. Therefore we are confident about finding 48 individuals with all 10 SNPs. If we don't find individuals with the 10 SNPs, we will mine the literature and find more SNPs that have a role in liver lipogenesis.

4.2

Intervention/Treatment procedures (by visits)

Phase2: Selection of 48 participants for the acute fructose challenge and 3-week intervention study:

The risk allele will be defined as the allele that is associated with higher levels of liver lipogenesis or fat as per previously published studies in Caucasians. The number of risk alleles will range from 0 to 20. The SNP will get a score of 2 with two risk alleles, 1 with one risk allele and 0 with no risk alleles. All the score will be added to get a cumulative score between 0 and 20 for 10 SNPs. We will select participants having > 15 risk alleles and < 6 risk alleles for our acute challenge and 3-week intervention study.

Phase 2&3- visit 1- MRI scan: The 48 individuals enrolled will visit the UNC NRI clinical suite run by the Human Research Core. After obtaining consent, they will be taken to the WakeForest Imaging center for baseline MRI scan. Studies have shown that 5-6% of liver fat is considered normal and anything more than that can reflect increased risk for fatty liver. If the MRI report of the participants shows liver fat > 6%, we will consult with the participant (if > 18years) and/or their parents in confidence and explain why they (or their child) cannot continue to

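### Aim 3 plans Pearson correlations without adjustment in a sample built from two genetic extremes and two age strata, so a correlation can reflect group differences rather than a relation within groups

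*Combined protocol and SAP*

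**What the plan says.** The synopsis sets Aim 3 as: "Determine the relationship between markers of DNL, liver fat accumulation and serum concentrations of lipids, uric acid and liver function markers", before and after the challenge. The method given is "data will be analyzed using students T test, and Pearsons correlations". Section 6.3 (Statistical Methods) lists paired t-tests, repeated measures regression and a regression on AUC, and does not mention correlations. The only covariate named anywhere is concomitant medication (section 4.5). No text conditions the Aim 3 correlations on genetic group or age.

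The sample is selected on the score. Section 4.2 says "We will select participants having > 15 risk alleles and < 6 risk alleles", and the synopsis (Study Phases, Screening) gives the age split: "more than 15 risk alleles and 12 children and 12 young adults with less than six number of risk alleles". The intervention text confirms "24 in each of the high and low genetic risk group". The SNPs were chosen for their "association with de novo lipogenesis (DNL) or liver fat accumulation in previously published studies in Caucasians".

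The Study Rationale predicts that "individuals with specific set of genotypes will be more susceptible to increased" de novo lipogenesis (DNL) and liver fat accumulation when all receive the same fructose. Serum lipids, uric acid and liver markers fall under the secondary objective, which only explores genetic-specific effects. One exclusion bears on the baseline values: "Liver fat fraction >5% as per baseline MRI scan".

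**The concern.** A Pearson correlation over all 48 people combines two things: how the markers move together among people of similar genetic risk, and how far apart the high- and low-risk means lie. Only the first says anything about a link between markers beyond the selection itself. Because the middle of the score distribution is left out, the second part can be larger than it would be in an unselected sample. The even split by age adds a second two-group structure that works the same way.

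Aim 3 could therefore report a relation between, say, liver fat and a serum lipid that only restates how participants were chosen, with a p-value that is too small for the within-group question. This matters even in an exploratory study. The stated purpose is preliminary data for a funding application, and section 6.4 intends the data for sizing larger studies. A correlation that depends on extreme-group sampling would not carry over to a differently sampled population.

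**Working it through.** **Inputs from the documents.** 4 cells of 12 = 24 high risk + 24 low risk = 48, which agrees with the stated total. The plan states no correlation, effect size, SD, alpha or sidedness, so it has no figure to reproduce.

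**Assumptions.** Two-sided 5% test; normally distributed markers; zero correlation within genetic group; marker means differing between groups by d1 and d2 within-group SDs. The range of d is assumed.

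**Expected pooled correlation.** With two equal halves, the group gap adds d1·d2/4 to the covariance and d²/4 to each variance, so

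r = (d1·d2/4) / √[(1 + d1²/4)(1 + d2²/4)].

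For d1 = d2 = 1.0: 0.25/1.25 = 0.20. For 1.5: 0.5625/1.5625 = 0.36. For 0.5: 0.0625/1.0625 = 0.06.

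**Rejection rates**, from 40,000 simulated studies of 24 + 24 for each row:

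| d1, d2 | Expected pooled r | Pooled test significant | Adjusted for group |
|---|---|---|---|
| 0.3, 0.3 | 0.02 | 5% | 5% |
| 0.5, 0.5 | 0.06 | 7% | 5% |
| 0.83, 0.83 | 0.15 | 17% | 5% |
| 1.0, 1.0 | 0.20 | 28% | 5% |
| 1.5, 1.5 | 0.36 | 76% | 5% |
| 0.5, 1.5 | 0.15 | 17% | 5% |
| 1.0, 0 | 0.00 | 5% | 5% |

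The effect depends on the product d1·d2. If one marker does not differ, it vanishes; if the differences have opposite signs, the artefact is a negative correlation.

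**Which d is relevant.** With 24 per group, the unpaired t-test has about 79% power at d = 0.8 and 93% at d = 1.0. At those differences the pooled correlation test rejects in about 15.5% and 28% of studies, which is 15.5/5 ≈ 3 and 28/5 ≈ 6 times nominal. So if the study finds clear group differences in two markers, their pooled correlation is already suspect.

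**Age stratum.** Suppose both markers differ by 0.8 SD between genetic groups and also by 0.8 SD between children and young adults. The expected pooled r is (0.16 + 0.16)/(1 + 0.16 + 0.16) = 0.24, and 40% of pooled tests are significant. Adjusting for genetic group alone leaves r = 0.16/1.16 = 0.14 and 16%. Adjusting for both gives 5%.

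**Price of adjusting.** The critical |r| is 0.285 unadjusted (46 df), 0.288 with group (45 df) and 0.291 with group and age (44 df).

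**The case against.** Four points can be made for the plan as it stands.

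- *Pooling is not stated.* A reader might infer that the plan commits to pooled correlations. It does not say so. The Aim 3 sentence opens by referring back to the earlier aims, which compare responses between and within the two groups, so a by-group reading is open. That reference could equally cover only the t-tests, and the plain reading of an unqualified Pearson correlation is a pooled one. The gap in specification stands either way.
- *Not every pair of markers is affected.* It is tempting to say that the design makes all these markers correlate. The hypothesis predicts group differences only in the DNL and liver fat responses. For lipids, uric acid and liver markers a difference is possible, since the SNPs were picked for a role in lipid metabolism, but it is not predicted. Both markers must differ for the artefact to arise. This limits the point to pairs where they do.
- *Baseline is constrained.* The 5% cap on liver fat, the exclusion of known hypertriglyceridemia and the single BMI band narrow the possible gap at week 0. This stands: the problem is likely smaller there than for week 3 values and changes, where the predicted difference in response would appear.
- *The target may be the pooled relation.* A pooled r really is non-zero in such a mixture, so a rejection is false only if the within-group relation is the question. Aim 3 does not say which is meant. But a pooled value from two selected tails has no clear population to describe, so the within-group relation is the more useful target.

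**Conclusion.** The point holds as a conditional one. As written, Aim 3 names a correlation analysis whose plain reading is confounded by the selection of participants, and nothing in the plan guards against it. The size depends on group differences that the documents do not give: practically none up to about 0.5 SD, roughly three to six times the nominal error rate between 0.8 and 1.0 SD, and most tests significant at 1.5 SD. These figures assume a two-sided 5% test, normal markers and no within-group correlation. The upper figures should not be read as what this study will show.

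A reader might also infer that the main result is compromised. It is not: the liver fat comparisons over time and between groups do not use these correlations. The consequence is confined to how an exploratory, non-primary aim is interpreted and reused.

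**What to change.** In the Aim 3 text and in section 6.3, replace the plain Pearson correlations with partial correlations (or the equivalent regression) adjusted for genetic group and age stratum. Carry them out separately for week 0 values, week 3 values and week 0 to 3 changes, since the aim asks about relations both before and after the challenge. Report confidence intervals, and show the correlations within each genetic group beside the adjusted ones. With 24 people per group the latter are descriptive: |r| must exceed 0.404 to reach two-sided 5%.

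The cost is one line of text and two degrees of freedom. No further data, visits or participants are needed.
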